3 STUDY DESIGN AND PLAN

3.1 Overall Study Design and Plan

This study is a Phase 1/2, first-in-human, open-label, dose-escalation and cohort expansion study designed to characterize the safety, tolerability, PK, pharmacodynamics, immunogenicity, and preliminary antitumor activity of MGC018 administered by IV infusion, alone (Module A) and in combination with MGA012 (Module B) (see [Figure 1](#)); Module B will commence only after the MTD or MAD of MGC018 monotherapy (Module A) has been defined. Each module of the study consists of a Dose Escalation Phase to determine the MTD (or MAD, if no MTD is defined), followed by a Cohort Expansion Phase to further define the safety and initial antitumor activity of the respective monotherapy (Module A) and combination (Module B) regimens, using doses defined in the Dose Escalation Phase of each respective module. Module B will commence only upon notification to all the study investigators/institutions.

Participants with relapsed/refractory, unresectable locally advanced, or metastatic solid tumors of any histology will be enrolled in the Dose Escalation Phase of each module. The Module A Cohort Expansion Phase will be limited to mCRPC, non-small cell lung cancer (NSCLC), triple negative breast cancer (TNBC), squamous cell carcinoma of the head and neck (SCCHN), and melanoma. The Module B Cohort Expansion Phase will be limited to specific cohorts of participants with SCCHN, mCRPC, and a cohort to be determined (TBD) at a later date, guided by evolving experience from the Dose Escalation Phase of the study.

[figure not shown]
MGC018 will be administered alone or in combination with MGA012 (also known as INCMGA00012), as illustrated below in [Figure 2](#) and [Figure 3](#), respectively. For Module A, MGC018 alone will be administered IV over 60 minutes on Days 1 and 22 of Cycle 1 and every subsequent 42-day cycle thereafter. For Module B, MGC018 alone will be administered IV over 60 minutes on Day 1 of Cycle 1 and with MGA012 on Day 22 of Cycle 1. Both MGC018 and MGA012 will be administered on Days 1 and 22 of every subsequent 42-day cycle thereafter, at the assigned dose for each cohort. Similar to MGC018, MGA012 will be administered IV over 60 minutes. On days when the MGC018 and MGA012 are to be administered on the same day (Module B only), MGA012 should be given first, followed immediately thereafter by MGC018.

For both the Dose Escalation Phase of Module A and Module B and the Cohort Expansion Phase of Module B, tumor assessments will occur at Day 42 of each cycle, for the first 4 cycles, and every other cycle thereafter. For the Cohort Expansion Phase of Module A, the tumor assessments will occur every 9 weeks (63 days). For Module A, the DLT evaluation period will be 21 days in duration; for Module B, the DLT evaluation period will be 42 days in duration. Participants who complete a given cycle, remain clinically stable, do not experience a DLT or other unacceptable toxicity, and do not otherwise meet the criteria for permanent treatment discontinuation may be eligible for additional treatment with MGC018 alone or in combination with MGA012 for up to a total of 18 cycles (approximately 2 years).

Following the last dose of study drug, all participants in Module A and Module B Cohort Expansion Phases will be followed every 3 months (90 days) for survival during a 2-year Survival Follow-up Period, until criteria are met for study discontinuation. Participants in Module A Dose Escalation Phase will be followed similarly for survival status until approval of Amendment 3, at which point they will be discontinued from follow up.

Figure 1

[figure not shown]
[figure not shown]
Overall Study Design

Note: MTD-2 = the dose level that is 2 dose levels below the MTD defined for MGC018 monotherapy.

MTD-1 = the dose level that is 1 dose level below the MTD defined for MGC018 monotherapy.

Abbreviations: mCRPC = metastatic castrate-resistant prostate carcinoma; MTD = maximum tolerated dose; NSCLC = non-small cell lung cancer; Q3W = every 3 weeks; RP2D = recommended phase II dose; SCCHN = squamous cell carcinoma of the head and neck; TBD = to be determined; TNBC = triple negative breast cancer.

Figure 2**MGC018 Monotherapy Dosing Schedule (Module A)****Figure 3****MGC018 and MGA012 Combination Dosing Schedule (Module B)**

3.2 Sample Size

The study plans to enroll approximately up to 182 participants (107 in Module A and 75 in Module B). This number of participants does not take into account participants who may be replaced for non-evaluable participants or the possibility of expanding the mCRPC cohort with an additional 24 participants at the discretion of the sponsor.

In Module A, 27 participants were enrolled, of which 26 participants were treated with MGC018 monotherapy in the Dose Escalation Phase. Up to 80 participants with mCRPC, NSCLC, TNBC, SCCHN, or melanoma (up to 16 in each) will be enrolled to the Cohort Expansion Phase of Module A. Up to an additional 4 participants may be added per cohort. In Module B, up to 27 participants will be enrolled in the Dose Escalation Phase based on a 3+3+3 design with planned 3 dose cohorts in MGC018 and MGA012 combination therapy. The Cohort Expansion Phase of Module B will enroll up to 16 participants into each of 3 tumor specific cohorts (SCCHN, mCRPC, and participants with a tumor type TBD at a later date) treated with MGC018 in combination with MGA012. The sample size for each tumor specific cohort is primarily based on providing preliminary estimation of responses. **Table 1** provides the 2-sided 95% confidence interval (CI) for a number of potential responses among 16 participants.

The sample size for the mCRPC cohort expansion is primarily based on providing preliminary estimation of a 6-month rPFS rate.

Table 1 **Response Rates and 95% Confidence Intervals**

Sample Size	Number of Responses	Response Rate (%)	95% Confidence Interval (%)
16	1	6.3	0.2, 30.2
16	2	12.5	1.6, 38.3
16	3	18.8	4.0, 45.6
16	4	25.0	7.3, 52.4
16	5	31.3	11.0, 58.7
16	6	37.5	15.2, 64.6

During the Cohort Expansion Phase, participants who withdraw before completing the first tumor assessment for a reason other than clinical disease progression or death are considered unevaluable for response. In these cases, additional participants may be enrolled.

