## 4.5.1 Participant Accrual

The maximum number of participants to be enrolled in this study will be approximately 182 participants. This number of participants does not take into account participants who may be replaced or the possibility of expanding the mCRPC cohort with an additional 24 participants at the discretion of the sponsor.

The number of participants enrolled in the Dose Escalation Phase cannot be precisely determined in advance and could range from 6 up to 54 participants depending on results in the course of the trial and the number of dose levels explored. This participant number does not take into account replacement of non-evaluable participants or the possibility of expanding an individual escalation cohort up to 15 participants to allow for further evaluation of safety, PK, and antitumor activity of the study drugs at the dose level in that cohort.

The Cohort Expansion Phase of the study will enroll up to 128 participants. Module A Cohort Expansion Phase will enroll up to 16 participants into each of 5 cohorts (mCRPC, NSCLC, TNBC, SCCHN, and melanoma) treated with MGC018 monotherapy. Module B will enroll up to 16 participants into each of 3 cohorts treated with the combination of MGC018 and MGA012: participants with unresectable, locally advanced or metastatic SCCHN, mCRPC, and participants with a tumor type TBD at a later date. During the Cohort Expansion Phase of the study, participants who withdraw before completing the first tumor assessment for a reason other than progression of disease may be considered unevaluable for response. In these cases, additional participants may be enrolled. In addition, up to 4 participants may be added per cohort.

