### **6.3 Blinding**

This is an open-label study.

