6.7 Efficacy Endpoint Analyses

6.7.1 Analyses of Response Endpoints

The number and percent of participants with their BOR will be summarized. The objective response rate (ORR) per RECIST v1.1 is estimated as the proportion of participants in the response evaluable population who achieve BOR of CR or PR. The 2-sided 95% exact binomial CIs of the response rates will be calculated.

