6.7.5 Analyses of Metastatic Castration-resistant Prostate Carcinoma-specific Endpoints

- rPFS: The censoring rules in [Table 2](#) will be applied to rPFS analysis. The analysis of rPFS will be the same as that described for PFS.
- PSA:

PSA response rate will be calculated for participants with a baseline PSA ≥ 2 ng/mL and at least 1 post-baseline value (i.e. PSA response evaluable population). The PSA response rate will be summarized at 12 weeks from baseline. The 2-sided 95% exact binomial CI of the response rate will be calculated.

The percent change in PSA from baseline overall time will be summarized by visit and presented individually by spider plot. The percentage of change in PSA from baseline to 12 weeks (or earlier if treatment is discontinued), and the best PSA percent change from baseline will be presented by waterfall plots.

The Kaplan-Meier method will be applied to estimate time to PSA progression in the PSA response evaluable population. PSA measurements are performed at baseline and then repeated prior to each dose of each treatment visit, approximately 30 days after the last study treatment administration (EOTV), and every 12 weeks (± 7 days) during the follow-up period until disease progression, start of another cancer therapy, or the study cutoff date, whichever comes first.

Participants without PSA progression at the time of analysis will be censored to the date of their last PSA assessment. The last three rules in **Table 2** will be applied to PSA progression analysis, with the changes from “progression” and “tumor assessment” to “PSA progression” and “PSA assessment”, respectively.

- SSE: SSE rate will be summarized. Specifically, SSE rate per 100 patient-year will be calculated as the number of each of the SSEs, including the occurrence of new symptomatic pathological fracture, use of external beam radiation to relieve bone pain, spinal cord compression, or tumor-related orthopedic surgical intervention, divided by the total patient-years in the mCRPC cohort. The Kaplan-Meier method will be applied to estimate time to SSE. Participants without SSE at the time of analysis will be censored at the last assessment. For each participant, the eCRF documenting any SSEs is scheduled to be completed pre-dose of each treatment. Participants without any SSE assessment will be excluded for the SSE endpoint analysis.

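### The optional mCRPC extension of 24 has no stated trigger and is analysed as one fixed sample; if good early results prompt it, the pooled rates in the extended cohort run high

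*SAP*

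**What the plan says.** SAP 3.2 and Protocol 14.1 plan expansion cohorts of up to 16, and the SAP's Table 1 "provides the 2-sided 95% confidence interval (CI) for a number of potential responses among 16 participants". The total of 182 does not count "the possibility of expanding the mCRPC cohort with an additional 24 participants at the discretion of the sponsor". Neither document gives a reason, a timing, a data cut-off or a criterion for using this option. Both modules have an mCRPC cohort of up to 16, and the documents do not say which one may gain the 24. Protocol 6.3 states: "This is an open-label study".

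The analysis sections do not mention the option:

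- SAP 6.7.1: ORR is "estimated as the proportion of participants in the response evaluable population who achieve BOR of CR or PR", and "The 2-sided 95% exact binomial CIs of the response rates will be calculated".
- SAP 6.7.5: for PSA response, "The 2-sided 95% exact binomial CI of the response rate will be calculated". rPFS is handled in the same way as PFS.
- SAP 6.7.2.1: Kaplan-Meier, with a log(-log) interval for the 6-month rate.

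Nothing separates participants enrolled before a decision to extend from those enrolled after it.

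**The concern.** A binomial proportion with an exact interval, and a Kaplan-Meier rate with a log(-log) interval, presume that the sample size does not depend on the outcomes. In an open-label study the sponsor can see PSA, scan and progression data on the first 16 before deciding whether to enrol 24 more. If a good run in those 16 is the reason for going on, that run stays in the pooled estimate.

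This matters most in mCRPC. It is the only tumor type with its own secondary objectives (rPFS and PSA response) and the only one with a 24-participant option. A reader of the report will know that the cohort was extended, so what matters is how the estimate behaves given extension. The plan offers no estimate protected against this selection, although the added 24 would supply one.

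**Working it through.** **Inputs from the documents.** Planned cohort n1 = 16; optional addition n2 = 24; two-sided 95% exact binomial interval (SAP 3.2, 6.7.1, 6.7.5).

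**Assumptions.** The plan gives no rule, so I assume extension when at least r of the first 16 respond. True rate p is varied, everyone is evaluable, and outcomes are independent.

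**Step 1: reproduce Table 1.** The lower limit is the 2.5% quantile of Beta(x, n-x+1) and the upper limit the 97.5% quantile of Beta(x+1, n-x). For n = 16 and x = 1 to 6 this gives 0.16-30.23, 1.55-38.35, 4.05-45.65, 7.27-52.38, 11.02-58.66 and 15.20-64.57. All six rows agree with the SAP to rounding.

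**Step 2: bias given extension.** The added 24 are independent of the first 16, so

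E(pooled | extended) = [16 × E(first-16 rate | extended) + 24 × p] / 40.

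The pooled bias is therefore 16/40 = 0.4 times the bias in the first 16, and the added 24 alone have none.

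Example: p = 20%, extend at 5/16 or more.

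- P(extend) = 0.20 and E(first-16 rate | extended) = 34.9%.
- E(pooled | extended) = (16 × 34.9 + 24 × 20)/40 = 26.0%, a bias of +6.0 points.
- The lower limit exceeds 20% in 7.8% of extended cohorts. Coverage given extension is 92.2%.

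A milder trigger does less. At p = 20% with 4/16 or more, the pooled rate is 24.0%, lower-limit error 4.5% and coverage 95.5%.

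**Step 3: averages.** Exact enumeration for 16 to 40, over true rates of 15-60%:

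| Extend if observed rate in first 16 is at least | Mean bias of pooled rate, given extension | Lower limit above truth, given extension |
|---|---|---|
| the true rate | +3.8 points | 3.3% |
| true rate + 5 points | +5.2 points | 4.8% |
| true rate + 10 points | +6.8 points | 7.3% |

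Nominal is 2.5%; a fixed sample of 40 gives about 1.7%.

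**Step 4: all outcomes, extended or not.** In the step 2 example, cohorts with 4/16 or fewer stop at 16. None of them has a lower limit above 20%, since 4/16 gives 7.27%. The overall lower-limit error is therefore about 0.20 × 7.8% = 1.6%, below nominal, and the overall bias is -1.8 points. For r = 1 to 9 and true rates of 5-70%:

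- overall bias runs from 0 to -3.0 points;
- lower-limit error never exceeds 2.5%;
- the lowest overall coverage is 93.3% to 95.0%, depending on r.

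**Step 5: 6-month rPFS rate.** Here I use the log(-log) interval and assume no censoring before 6 months. At a true rate of 40%, extending at 8/16 or more event-free, the pooled rate is 6.0 points too high given extension, with coverage 94.0%. Over all outcomes (true rates 30-60%, r = 5 to 10), coverage runs from 90.3% to 97.2%, against 93.8% to 96.7% for a fixed 16 or 40. At the 90.3% point (true 60%, r = 7) the lower limit exceeds the truth only 1.6% of the time, so the shortfall comes from intervals lying too low.

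**The case against.** The strongest reply is that dependence on results is assumed. No passage says that mCRPC data will be looked at before the option is used. SAP 3.2 ties the mCRPC size to estimating the 6-month rPFS rate, which could be a pure precision reason. This stands: an extension for precision, accrual or any other reason unrelated to outcomes causes no bias. But the documents do not give that reason for the 24. The same protocol lets emerging activity guide the third Module B tumor type (4.1.2) and lets response data inform the expansion dose (4.3). A reader cannot rule out a results-driven extension.

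A reader might also infer that the plan's 95% intervals lose their level in general. Step 4 does not support that for the exact intervals. Under an extend-if-good rule the lower-limit error stays within 2.5% over all outcomes, and the average bias is downward because poor cohorts stay at 16. Pooling also dilutes an excess already present in the first 16.

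A further inference would be type I error inflation, for instance from adding participants until a lower limit clears a benchmark. The documents contain no benchmark, null rate, test or success threshold. Cohort sizes rest on preliminary estimation, and the primary objective is safety and dose.

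Finally, the same argument could be turned on the smaller option: "Up to an additional 4 participants may be added per cohort" (SAP 3.2, in the Module A text; Protocol 4.5.1 applies it to expansion cohorts generally). A separate estimate from at most four participants would tell nobody anything, so the recommendation stops at the 24.

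**Conclusion.** The gap is real but conditional. The documents give a discretionary, open-label extension with no criterion, and a fixed-sample analysis of the pooled cohort. If good early results prompt the extension, the pooled response rate in the extended cohort is too high by about 4 to 7 points on average under the triggers tried, and the lower limit overshoots the truth in about 3% to 7% of such cohorts. For the 6-month rPFS rate the one case worked in step 5 gives +6.0 points. All these figures rest on assumed triggers, full evaluability and, for rPFS, no early censoring.

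The documents do not support the stronger conclusions that the sponsor will extend on good results, that the reported rates are overstated on average, or that a test level is inflated. What is at stake is the reading of descriptive secondary estimates. That justifies a small reporting change and no redesign.

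**What to change.** Add to SAP 6.7.1, 6.7.2 and 6.7.5 wording such as: *If the 24-participant mCRPC extension is used, ORR, PSA response rate and the 6-month rPFS rate will be reported for the added participants alone and for all mCRPC participants of that module. The pooled confidence intervals will be footnoted as not adjusted for the decision to extend.*

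In the CSR, record the reason for the extension and the data cut-off available when it was decided. In SAP 3.2 and Protocol 14.1, state whether the 24 belong to the Module A or the Module B mCRPC cohort.

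The cost is a SAP paragraph, one clarifying sentence in each document and a few table columns, with no extra participants or procedures. The drawback is precision. At an observed 50%, the exact 95% interval is 29.1-70.9% for n = 24 against 33.8-66.2% for n = 40, and it is wider still if some of the 24 are not evaluable. The added-participant estimate therefore accompanies the pooled one and does not replace it.

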4 ANALYSIS POPULATIONS

4.1 Analysis Populations

The study analyses will be performed on the following populations:

- Safety Population: All participants who received at least one dose of any study drug. This population will be used for analyses of safety, pharmacodynamics, and immunogenicity. It will also be used for summary of baseline data and analyses of PFS, rPFS, and OS.
- Response Evaluable Population: All participants who received at least one dose of any study drug, had baseline measurable disease, and had at least one post-baseline radiographic tumor assessment or discontinued treatment due to clinical progressive disease or death. This population will be used for summary of tumor assessment data and analyses of response rates.
- PSA Response Evaluable Population: mCRPC participants with a baseline PSA \geq 2 ng/ML and at least 1 post-baseline PSA measurement. This population will be used to calculate and summarize the PSA response rates.

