## 9.16 End of Treatment Visit

A list of evaluations to be performed for the EOTV is provided in [Appendix 1](#). The EOTV should be performed after the participant has met study treatment discontinuation criteria specified in [Section 5.4](#); the visit should be performed within 30 days following the last dose of study drug. It is recognized that certain participants (such as those experiencing progression of disease) may be cared for in facilities other than the participating study site, may proceed to receive other cancer therapy, and/or may elect not to return to the study site. Therefore, this visit is considered optional, but should be carried out whenever possible. All required procedures and tests should be performed if the visit is performed. Note: the tumor assessment will not be performed at the EOTV for participants who had a previous scan performed < 28 days of the EOTV.

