## 14 STATISTICAL ANALYSIS

This section outlines the statistical methodology and principles which will be used for data analysis in this study. A separate statistical analysis plan (SAP) and statistical programming plan (SPP) will further describe the details regarding statistical methods and will govern the analysis. Analyses will be performed for MGC018 alone and in combination with MGA012 respectively.

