## 14.2 Analysis Populations

The study analyses will be performed on the following populations:

- Safety Population: All participants who received at least one dose of study drug. This population will be used for analyses of safety, pharmacodynamics, and immunogenicity. It will also be used for summary of baseline data and analyses of PFS, rPFS, and OS.
- Response Evaluable Population: All participants who received at least one dose of study drug, had baseline measurable or non-measurable disease, and had at least one post-baseline radiographic tumor assessment or discontinued treatment due to clinical progressive disease or death. This population will be used for summary of tumor assessment data and analyses of response rates.
- PSA Response Evaluable Population: mCRPC participants with a baseline PSA  $\geq 2$  ng/mL and at least 1 post baseline PSA measurement. This population will be used to calculate and summarize PSA response rates.

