## **2 Tumor Response Evaluation**

### **2.1 Assessment of overall tumor burden and measurable disease**

To assess objective response or future progression, it is necessary to estimate the *overall tumor burden at baseline* and use this as a comparator for subsequent measurements. Only patients with measurable disease at baseline should be included. Measurable disease is defined by the presence of at least one measurable lesion (as detailed above).

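### ORR drops treated participants who never have a post-baseline scan unless they stopped for clinical progression or death, and no all-treated ORR is planned beside it

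*SAP*

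**What the plan says.** SAP 4.1 defines the Response Evaluable Population as participants with at least one dose who "had baseline measurable disease, and had at least one post-baseline radiographic tumor assessment or discontinued treatment due to clinical progressive disease or death". SAP 6.7.1 then has ORR "estimated as the proportion of participants in the response evaluable population who achieve BOR of CR or PR". SAP 6.1 and Protocol 14.2 and 14.6.1 use the same set for response rates. The Safety Population, which is everyone dosed, is assigned PFS, rPFS and OS but not ORR.

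On early drop-outs in the expansion cohorts, SAP 3.2 states that "participants who withdraw before completing the first tumor assessment for a reason other than clinical disease progression or death are considered unevaluable for response" and lets further participants be enrolled in their place. Protocol 14.1 agrees. The protocol synopsis and section 4.5.1 word the rule differently: there, withdrawal before the first assessment "for a reason other than progression of disease may be considered unevaluable for response".

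The end-of-treatment visit could supply a scan, but Protocol 9.16 says of it: "Therefore, this visit is considered optional, but should be carried out whenever possible".

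The two documents also differ on who belongs in the set. Protocol 14.2, like the synopsis, takes participants who "had baseline measurable or non-measurable disease, and had at least one post-baseline radiographic tumor assessment", whereas SAP 4.1 requires measurable disease. Protocol 14 says the SAP and the programming plan "will further describe the details regarding statistical methods and will govern the analysis".

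**The concern.** Entry to the ORR denominator depends on what happens after dosing. A participant without a scan is kept as a non-responder if treatment stopped for clinical progression or death. One who stops for toxicity or intolerance, or who withdraws, is dropped. A person with no scan cannot be a responder, so each exclusion removes a certain non-response from the denominator and nothing from the numerator. The error therefore runs in one direction only, and it grows with early drop-out for intolerance, in a study whose primary objective is safety and tolerability.

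The tumor-specific cohorts, other than mCRPC, are sized to give a preliminary estimate of response, so ORR is the figure readers will take from them. Disposition and adverse-event tables will show the drop-outs, but no planned table gives the all-treated rate with its interval.

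The measurable-disease mismatch is a separate point that affects the same denominator. It matters in mCRPC, where Protocol 5.1 (criterion 6) allows enrolment without measurable disease.

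**Working it through.** **Inputs.** The cohort size of 16, the allowance of up to 4 added participants per cohort, and replacement of unevaluable participants come from SAP 3.2. The two-sided 95% exact binomial interval comes from SAP 6.7.1. The number excluded, k, is not in the documents. I assume k = 1 to 4. Four responders is an illustrative row of SAP Table 1. All participants in the example are taken to have measurable disease.

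**The plan's own figures.** With x responders among n, the exact limits are the 0.025 quantile of Beta(x, n − x + 1) and the 0.975 quantile of Beta(x + 1, n − x). For n = 16 and x = 1 to 6 these reproduce all six rows of SAP Table 1 (Protocol Table 10) to one decimal. For example, 4/16 = 25.0% (7.3, 52.4), a width of 52.4 − 7.3 = 45.1 points.

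**Case A: exclusions replaced until 16 are evaluable.** Reported ORR is 4/16 = 25.0% (7.3, 52.4). All-treated ORR is 4/(16 + k).

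| k | All-treated ORR (95% CI) | Reported minus all-treated |
|---|---|---|
| 1 | 4/17 = 23.5% (6.8, 49.9) | 1.5 |
| 2 | 4/18 = 22.2% (6.4, 47.6) | 2.8 |
| 3 | 4/19 = 21.1% (6.1, 45.6) | 3.9 |
| 4 | 4/20 = 20.0% (5.7, 43.7) | 5.0 |

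**Case B: 16 treated, none replaced.** All-treated ORR is 4/16 = 25.0% (7.3, 52.4). Reported ORR is 4/(16 − k).

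| k | Reported ORR (95% CI) | Reported minus all-treated |
|---|---|---|
| 1 | 4/15 = 26.7% (7.8, 55.1) | 1.7 |
| 2 | 4/14 = 28.6% (8.4, 58.1) | 3.6 |
| 3 | 4/13 = 30.8% (9.1, 61.4) | 5.8 |
| 4 | 4/12 = 33.3% (9.9, 65.1) | 8.3 |

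**Relative size in Case A.** (x/16) ÷ (x/(16 + k)) − 1 = k/16. That is 6.25% per excluded participant, whatever the number of responders.

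**Can it happen?** In Module A expansion the first scan is due at 63 days, after doses on Study Days 1, 22 and 43 (Protocol Appendix 1), so there are about nine weeks in which a participant can leave unscanned. The category NE in SAP 5.1.1 does not help, because BOR enters ORR only within the evaluable set. SAP 6.2 treats missing data as missing and has no non-responder rule. The only efficacy sensitivity analysis in the SAP is for PFS (6.7.2.1).

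**Which definition operates?** The SAP governs, and Protocol Appendix 5, section 2.1 points the same way: "Only patients with measurable disease at baseline should be included". That support is limited, because Appendix 5 also opens by requiring a measurable lesion of every participant, which conflicts with the mCRPC exception in criterion 6. The SAP definition is operative, but the protocol text is unreconciled.

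**The case against.** The strongest reply is that few participants would be lost this way. SAP 4.1 does not require the scan to be on treatment. Protocol 9.17 and 11.1.1 provide three-monthly contact on response status after treatment stops for reasons other than progression, and 9.17 allows outside CT results to be entered. Protocol 12.2.2 keeps participants who stop drug for a related immediately reportable event on study for safety and efficacy observation. This narrows the problem, but entry of post-treatment scans is discretionary and none of these provisions guarantees one.

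SAP 3.2 speaks of participants who withdraw, so replacement is not clearly allowed for someone who stops drug but stays on study. That affects which case above applies. It does not affect the exclusion, which follows from SAP 4.1. For the same reason, the two wordings of who is unevaluable affect replacement more than the ORR set.

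The contrast with PFS and rPFS is weaker than it looks. Under SAP Table 2, a participant with no post-baseline scan who did not die before the first scheduled one is censored at first dose and contributes almost nothing. Only OS makes real use of such participants.

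Counting unscanned participants as failures is also a convention. The evaluable-set rule is pre-specified, ORR is descriptive, and the mCRPC expansion is sized on 6-month rPFS. A reader could approximate the all-treated rate from treated and responder counts. These points are reasons to keep the planned ORR, and they do not argue against reporting a second one.

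**Conclusion.** The concern holds. ORR is planned only in the Response Evaluable Population, and a treated participant with measurable disease who is never scanned and did not stop for clinical progression or death is outside it. No all-treated ORR appears in either document. The programming plan was not available, but SAP 7 ties its tables to the analyses described in the SAP, and Protocol 14.8 says additional analyses will be in the SAP.

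Exclusion is possible, not automatic. With one or more exclusions and at least one responder, the direction is certain. The size depends on assumed counts: one exclusion among 16 costs under 2 points, and the 8.3-point figure needs 4 of 16 treated participants unscanned with none replaced. No test or threshold rests on ORR, so error rates are unaffected. The change should be made because it is cheap and removes a one-directional upward bias, not because a conclusion would fall without it.

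**What to change.** Add to SAP 6.7.1: *ORR with exact 95% CI will also be reported in all treated participants with measurable disease at baseline. Participants with no post-baseline scan are counted as non-responders (BOR = NE), and participants who were replaced are included.* Present it beside the response-evaluable ORR, with the number excluded and the reasons. This denominator also settles how mCRPC participants without measurable disease are handled.

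Align the evaluable-set definition in the protocol synopsis and section 14.2 with SAP 4.1 on measurable disease. Align the synopsis and section 4.5.1 with Protocol 14.1 and SAP 3.2 on who is unevaluable.

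The cost is one SAP sentence, one table and a protocol wording clarification. No new data are needed, since NE is already a BOR category. The only downside is a second, slightly lower ORR to report.
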